There is also evidence that fibrinogen-like protein 1 (FGL-1), a liver-secreted protein, is a major LAG-3 functional ligand independent from major histocompatibility complex (MHC) Class II. FGL-1 inhibits antigen-specific T-cell activation, and ablation of FGL-1 in mice promotes T-cell immunity. Blockade of the FGL-1:LAG-3 interaction by monoclonal antibodies stimulates tumor immunity and is therapeutic against established mouse tumors in a receptor-ligand, inter-dependent manner. FGL-1 is highly produced by human cancer cells, and elevated FGL-1 in the plasma of cancer patients is associated with a poor prognosis and resistance to anti-PD-1/B7-H1 therapy.

Nivolumab is currently in development and has been registered in a variety of tumors. Development of nivolumab for HCC was initiated in 2012 with CA209040, which is a Phase 1/2 clinical trial evaluating the safety and efficacy of nivolumab in advanced HCC. Data from the dose-escalation and expansion cohorts of this study led initially to the accelerated approval of nivolumab for the second-line (2L) therapy of advanced HCC patients who progressed on or were intolerant to sorafenib in many, but not all (eg, not approved in Japan), countries. As of the most recent analysis, with 27 months of follow-up, with 154 participants treated with nivolumab 3 mg/kg every 2 weeks (Q2W), the objective response rate (ORR) was 14%, the median progression-free survival (mPFS) was 2.83 months, and the median OS (mOS) was 15.6 months.

Most recently, the doublet combination of nivolumab and ipilimumab received accelerated approval in the United States in the same setting in HCC. This approval was based on data from the 28-month follow-up, demonstrating an ORR of 33% among the 49 participants treated with nivolumab 1 mg/kg + ipilimumab 3 mg/kg every 3 weeks (Q3W) for 4 doses, followed by nivolumab 240 mg Q2W.

After the approval of atezolizumab and bevacizumab combination in 1L HCC, the treatment recommendations shifted to indicate that previously approved 1L TKI therapies are now recommended after atezolizumab and bevacizumab therapies, and agents that were recommended after failure of 1L TKI therapies are now recommended in subsequent settings, according to the most recent guidelines. Although, for patients who are not eligible or cannot get access to atezolizumab and bevacizumab regimen, the recommendations remain the same. Recommendations for 2L therapy differ depending on which regimen was administered 1L.

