3.1.1 Research Hypothesis

It is anticipated that relatlimab in combination with nivolumab will demonstrate a favorable benefit/risk profile compared to nivolumab monotherapy to support further clinical testing in IO treatment-naïve advanced/metastatic HCC patients.

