CA224047, a global, double-blind, randomized, Phase 2/3 study comparing a fixed-dose combination (FDC) formulation of nivolumab 480 mg + relatlimab 160 mg FDC Q4W to nivolumab 480 mg Q4W in participants with previously untreated advanced melanoma demonstrated a statistically significant and clinically meaningful benefit by dual inhibition of the LAG-3 and PD-1 pathways.^{45, 46} The study achieved its primary endpoint, demonstrating statistically significant improvement in progression-free survival (PFS) by BICR with nivolumab 480 mg + relatlimab 160 mg FDC Q4W compared to nivolumab monotherapy in all randomized participants (N = 714) (PFS hazard ratio [HR] = 0.75 [95% CI: 0.62, 0.92], P-value = 0.0055). With a median follow-up of 13.2 months, the median PFS in the nivolumab + relatlimab FDC (3:1) group was 10.1 months (95% CI, 6.4–15.7) compared to 4.6 months (95% CI, 3.4–5.6) in the nivolumab monotherapy arm. PFS rates at 12 months were 47.7% (95% CI, 41.8–53.2) and 36.0% (95% CI, 30.5–41.6) for nivolumab + relatlimab FDC (3:1) and nivolumab monotherapy, respectively. The PFS benefit of nivolumab + relatlimab FDC (3:1) was consistent across key prespecified subgroups. The secondary endpoint of overall survival (OS) showed clinically meaningful improvement with nivolumab + relatlimab FDC over nivolumab monotherapy (median OS non-estimable [34.20, not reached {NR}]) versus 34.1 months [25.23, NR]; HR = 0.80 [0.64–1.01]; p = 0.0593) in all randomized participants but was not statistically significant.^{45,46}

Due to the statistical non-significance of the secondary endpoint of OS, ORR was not formally tested per the statistical testing hierarchy; however, clinically meaningful numerical differences were observed with the nivolumab + relatlimab FDC arm over nivolumab monotherapy (43.1% vs 32.6%).⁴⁷

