4 OBJECTIVES AND ENDPOINTS

Objectives and endpoints are presented in Table 4-1.

Table 4-1: Objectives and Endpoints

Objective	Endpoint
Primary	

 To evaluate the efficacy of relatlimab in combination with nivolumab relative to nivolumab monotherapy in IO therapy-naive participants after prior treatment with TKI therapy 	
 ORR assessed by BICR using RECIST v1.1
Key Secondary	

 To investigate safety and tolerability of relatlimab in combination with nivolumab in participants with advanced HCC 	
 Incidence of AEs, SAEs, and AEs leading to discontinuation, deaths, and clinical laboratory test abnormalities

 To further evaluate the preliminary efficacy of relatlimab in combination with nivolumab 	
 DCR, DOR, and PFS assessed by BICR per RECIST v1.1 ORR, DCR, DOR, and PFS assessed by Investigator per RECIST v1.1 OS

Table 4-1: Objectives and Endpoints

Objective	Endpoint

Abbreviations: AE = adverse event; BICR = Blinded Independent Central Review; [redacted]
DCR = disease control rate; DOR = duration of response; [redacted]
[redacted] HCC = hepatocellular carcinoma;
[redacted] IO = immuno-oncology; [redacted]
[redacted] ORR = objective response rate; OS = overall
survival; PFS = progression-free survival; [redacted]
[redacted] RECIST = Response Evaluation Criteria in Solid Tumors; SAE = serious adverse event; [redacted]
[redacted] TKI = tyrosine kinase inhibitor.

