7.1 Treatments Administered

The selection and timing of dose for each participant is provided in Table 7.1-1.

Table 7.1-1: Treatments Administered

Study Arm	Study Treatment	Dose Level	Frequency of Administration and Duration of Treatment	Route of Administration	Approximate Infusion Time, minutes
Arm A	Nivolumab	480 mg	Q4W Until progression, unacceptable toxicity, or withdrawal of consent	IV	30
Arm B	Nivolumab/ Relatlimab ^a	480 mg/ 480 mg	Q4W Until progression, unacceptable toxicity, or withdrawal of consent	IV	60
Arm C	Nivolumab/ Relatlimab ^a	480 mg/ 960 mg	Q4W Until progression, unacceptable toxicity, or withdrawal of consent	IV	60 ^b

Abbreviations: IV = intravenous; mg = milligram; Q4W = every 4 weeks.

^a Nivolumab and relatlimab are co-administered.

^b Infusions will occur over approximately 60 minutes for participants weighing equal to or greater than 45 kg, and for participants weighing less than 45 kg, infusions will occur over approximately 90 minutes.

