8.1.2 Treatment Beyond Disease Progression

Accumulating evidence indicates a minority of participants treated with immunotherapy may derive clinical benefit despite initial evidence of progressive disease.⁴³

Participants treated with study therapy in any arm will be permitted to continue treatment beyond initial RECIST v1.1-defined progressive disease, assessed by the Investigator, as long as they meet the following criteria:

- Investigator-assessed clinical benefit.
- Tolerance of study treatment.
- Stable performance status.
- Treatment beyond progression will not delay an imminent intervention to prevent serious complications of disease progression (eg, CNS metastases).
- Participant provides written informed consent prior to receiving additional treatment. All other elements of the main consent including description of reasonably foreseeable risks or discomforts, or other alternative treatment options will still apply.

Radiographic assessment/scan(s) should continue in accordance with the [Section 2](#) (Schedule of Activities) for the duration of the treatment beyond progression and should be submitted to the central imaging vendor.

If the Investigator feels that the participant continues to achieve clinical benefit by continuing treatment, the participant should remain on the trial and continue to receive monitoring according to [Section 2](#) (Schedule of Activities).

For the participants who continue study therapy beyond progression, further progression is defined as an additional 10% increase in tumor burden with a minimum 5 mm absolute increase from time of initial progressive disease. This includes an increase in the sum of diameters of all target lesions and/or the diameters of new measurable lesions compared to the time of initial progressive disease. Treatment should be discontinued permanently upon documentation of further progression.

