9.2.2 Method of Detecting AEs and SAEs

AEs can be spontaneously reported or elicited during open-ended questioning, examination, or evaluation of a participant. Care should be taken not to introduce bias when collecting AEs and/or SAEs. Inquiry about specific AEs should be guided by clinical judgement in the context of known AEs, when appropriate for the program or protocol.

Every AE must be assessed by the Investigator with regard to whether it is considered immune-mediated. For events which are potentially immune-mediated, additional information will be collected on the participant's CRF.

All non-serious AEs (not only those deemed to be treatment-related) should be collected continuously during the treatment period and for a minimum of 135 days following discontinuation of study treatment.

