10.3.2 Safety Analyses

All safety analyses described in Table 10.3.2-1 will be performed on the treated population.

[figure not shown]
Table 10.3.2-1: Safety Analyses

Endpoint	Statistical Analysis Methods
Primary	Not applicable.
Secondary	Incidence of AEs, SAEs, AEs leading to discontinuation, death, and laboratory abnormalities will be analyzed using frequency statistics.

Abbreviations: AE = adverse event; IMAE = immune-mediated adverse event; SAE = serious adverse event.

[figure not shown]
[figure not shown]

[figure not shown]

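### In the visible text the AE endpoints are summarised only as crude frequencies although time at risk depends on treatment, so Arm A and Arm B percentages read side by side can mislead in either direction

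*Combined protocol and SAP*

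**What the plan says.** Table 4-1 lists as a key secondary endpoint "Incidence of AEs, SAEs, and AEs leading to discontinuation, deaths, and clinical laboratory test abnormalities". Table 10.3.2-1 gives the method, applied to the treated population: "Incidence of AEs, SAEs, AEs leading to discontinuation, death, and laboratory abnormalities will be analyzed using frequency statistics". No person-time or time-to-event measure for AEs appears in the visible text. By contrast, Table 10.3.1-1 assigns the Kaplan-Meier method to DOR, PFS and OS.

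Three provisions determine how long a participant is observed for AEs:

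- Table 7.1-1 gives the same treatment duration in every arm: "Until progression, unacceptable toxicity, or withdrawal of consent".
- Under Section 8.1.2, participants in any arm who meet the listed criteria "will be permitted to continue treatment beyond initial RECIST v1.1-defined progressive disease".
- Under Section 9.2.2, non-serious AEs "should be collected continuously during the treatment period and for a minimum of 135 days following discontinuation of study treatment". Section 9.2.1 uses the same 135 days for SAEs, with an exception once new anti-neoplastic therapy has started. Deaths, and SAEs suspected to be related to study treatment, are still reported after that point.

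Section 3.1.1 sets the context: the combination is expected to show that it "will demonstrate a favorable benefit/risk profile compared to nivolumab monotherapy". Section 10.3 describes itself as a summary and leaves detail to an SAP to be finalised before database lock.

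**The concern.** A crude percentage answers how many participants had an event while they were being watched. Here the length of watching is itself a result of treatment. If the combination delays progression, Arm B is observed for longer and collects more events at the same event rate. If Arm B stops earlier because of toxicity, it is observed for less time and added harm can be hidden.

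The stake is the risk half of the benefit/risk statement in Section 3.1.1. Even with no formal test, the two columns of AE percentages will be read against each other, and the reader cannot tell toxicity from time on treatment.

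**Working it through.** **The plan's own figures.** The AE endpoints carry no stated figure. The only visible safety number is the monitoring boundary in Section 3.3.3: 29 of 100, for a posterior probability above 95% that the treatment-related SAE rate exceeds 22%. The prior is not visible. With Beta(1,1) assumed, the probability is 0.931 at 28 and 0.956 at 29, so the boundary reproduces. It plays no part below, except that 22% is reused as an example incidence.

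**Inputs**

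- Arm A time on treatment: the Synopsis reports that "the median progression-free survival (mPFS) was 2.83 months" for nivolumab in the earlier HCC study. Exponential PFS stands in for time on treatment.
- Effect of relatlimab on progression: "PFS hazard ratio [HR] = 0.75" (Section 3.2.3), from untreated melanoma at a different relatlimab dose. It is used only as an illustration.
- Post-treatment window: 135 days, or 4.44 months.
- Participants: 226 in Arms A and B (Section 5.2), taken as 113 per arm. The early 2:1:2 allocation may make the true split slightly different.
- AE hazard λ: not in the documents. It is assumed constant and identical in both arms, so the true rate ratio is 1.

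**Formula.** μ_A = ln 2 / 2.83 = 0.245 per month and μ_B = 0.75 × μ_A = 0.184. Mean time on treatment, 1/μ, is 4.08 months in Arm A and 5.44 in Arm B. Mean observation with the 135 days added is 8.52 and 9.88 months. Crude incidence over the full window is

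1 − exp(−4.44λ) × μ/(μ+λ).

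- λ = 0.05 per month: Arm A 1 − 0.801 × 0.830 = 33.5%; Arm B 1 − 0.801 × 0.786 = 37.0%. The gap is +3.6 points before rounding.
- λ = 0.10 per month: Arm A 1 − 0.642 × 0.710 = 54.4%; Arm B 1 − 0.642 × 0.648 = 58.4%. The gap is +4.0 points.

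With λ set to give a chosen Arm A incidence, Arm B shows:

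| Arm A | HR 0.75 | HR 0.60 | HR 0.50 |
|---|---|---|---|
| 22% | 24.7% | 27.3% | 29.7% |
| 50% | 54.0% | 57.5% | 60.4% |
| 80% | 82.7% | 84.8% | 86.4% |

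**Opposite direction.** If Arm B stops treatment at 1.5 times the Arm A rate (μ_B = 0.367) with λ = 0.10, its crude incidence is 49.6% against 54.4%. It looks about 5 points safer with no difference in hazard.

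**Hazard shape.** Take Arm A at 22% and the 135-day window. If events can occur only in the first 3 months, the gap is 0, because the post-treatment window alone covers that period. If they can occur only in the first 6 months, the gap is 0.2 points at HR 0.75 and 0.4 at HR 0.50.

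**Window.** Counting on-treatment events only, incidence is 1 − μ/(μ+λ), and the gaps at HR 0.75 are +4.4 points (λ = 0.05) and +6.3 points (λ = 0.10). Section 9.2.2 does not define AEs that way. The formula does suit AEs leading to discontinuation, which cannot arise after treatment has stopped. With Arm A at 10%, Arm B shows 12.9%.

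**Sampling error.** At 113 per arm, the standard error of 37.0% minus 33.5% is √(0.335 × 0.665/113 + 0.370 × 0.630/113) = 6.4 points. At 22% in both arms it is 5.5 points.

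**The case against.** Several counter-arguments stand.

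- A reader might infer that the plan has no exposure-aware safety analysis at all. The documents do not support that. Section 10.3 is a summary, no SAP text is in the public document, the text of Section 10.3.3 is not shown, and the footnote to Table 10.3.2-1 defines immune-mediated AEs although no such row is visible. The point covers the visible text only.
- A reader might infer a biased formal comparison. None is specified. The primary objective is worded relative to nivolumab monotherapy; the safety objective is not. The problem lies in reading descriptive percentages side by side.
- A reader might infer that Arm B will look worse if relatlimab works. The direction is not fixed, because earlier stopping for toxicity pushes the other way.
- The size rests on a constant hazard and on a hazard ratio from another tumour and dose. It is below one standard error and nearly vanishes for early-onset events.
- The model does not represent the SAE exception after new anti-neoplastic therapy, or death before day 135. A shorter SAE window would move the gap towards the on-treatment figures.
- Person-year rates have a bias of their own: they can dilute early toxicity in the arm with longer exposure. They should not be the main basis of the safety statement.

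What survives is that the distortion is systematic, so more participants would not remove it. Crude percentages also cannot show whether events were early, where the artefact is negligible, or accrued steadily, where it is not.

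**Conclusion.** The point holds as a worthwhile, low-cost improvement; it does not threaten the study's conclusions. In the visible text, AEs, SAEs and AEs leading to discontinuation are reported as crude frequencies over a period whose length depends on efficacy and tolerability.

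Under an identical constant hazard, a 2.83-month control median and a PFS hazard ratio of 0.75, the artefact over the full window is about 3 to 4 points. It grows to roughly 8 to 10 points at a hazard ratio of 0.50 with Arm A at 22% or 50%, reverses if Arm B stops sooner, and is near zero for events confined to the first 3 to 6 months. The argument does not apply to deaths, which delayed progression may reduce.

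**What to change.** Keep the crude frequencies. Add the following to Table 10.3.2-1 or the SAP before database lock:

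- (a) Duration of exposure and duration of AE observation, by arm.
- (b) Cumulative incidence of first AE, first SAE and first AE leading to discontinuation at a fixed time such as 6 months, with death as a competing event. Make this the main display for reading Arm B against Arm A. For AEs leading to discontinuation, stopping treatment for another reason should also count as a competing event. State how participants whose AE window closes before the chosen time are handled: at 6 months (about 183 days) this affects treatment ending before about day 48 (183 − 135), whereas a time of 135 days or less avoids it.
- (c) Exposure-adjusted incidence rates as supportive, with person-time matching the actual collection window, including the SAE exception in Section 9.2.1.

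The cost is SAP wording and a few tables; the dosing and AE dates should already be collected. The downside is that the rates in (c) assume a roughly constant hazard and can dilute early-onset toxicity, which is why (b) leads. If the SAP already contains these displays, the sponsor need only confirm it.

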10.3.4 Interim Analyses

10.3.4.2 Bayesian Continuous Monitoring for Safety

A Bayesian continuous monitoring framework⁷² will be utilized to detect safety signals that occur during the study that may lead to termination of Arm B or Arm C.

These boundaries can be applied in a continuous basis (does not require the exact number of participants [REDACTED]) and is intended to assist on the recommendation to the BMS SC for clinical interpretation. Other parameters may be considered, and other posterior probabilities and boundaries may be calculated, as deemed appropriate by the SC, without amending the protocol.

The SAP will further describe the planned interim analyses.

12 APPENDICES

APPENDIX 1 ABBREVIATIONS AND TRADEMARKS

Term	Definition
–	negative
+	positive
°C	degrees Celsius
µg	microgram
µL	microliter
1L	first line
2D	2-dimensional
2L	second line
3L	third line
AASLD	American Association for the Study of Liver Disease
AE	adverse event
AIDS	acquired immunodeficiency syndrome
AFP	alpha-fetoprotein
ALP	alkaline phosphatase
ALT	alanine aminotransferase
APASL	Asian Pacific Association for the Study of the Liver
aPTT	activated partial thromboplastin time
AR	additional research
ART	antiretroviral therapy
AST	aspartate aminotransferase
BCLC	Barcelona Clinic Liver Cancer
Bcl-xL	B-cell lymphoma-extra large
BIC	Bayesian information criterion
BICR	blinded independent central review
BMI	body mass index
BMS	Bristol Myers Squibb

Term	Definition
BP	blood pressure
BSC	best supportive care
BTLA	B- and T-lymphocyte attenuator
BUN	blood urea nitrogen
Cavg	average concentration
CBC	complete blood count
CD	cluster of differentiation
CFR	Code of Federal Regulations
cHL	classical Hodgkin lymphoma
CI	confidence interval
CIOMS	Council for International Organizations of Medical Sciences
CL	clearance
CLss	steady-state clearance
Cmax	maximum concentration
Cmaxss	steady-state maximum concentration
CMV	cytomegalovirus
CNS	central nervous system
CONSORT	Consolidated Standards of Reporting Trials
COVID-19	coronavirus disease 2019
CR	complete response
CrCl	creatinine clearance
CRF	case report form, paper or electronic
CRO	contract research organization
CSR	clinical study report
CT	computed tomography
CTAg	clinical trial agreement
CTCAE	Common Terminology Criteria for Adverse Events

Term	Definition
CTLA-4	cytotoxic T-lymphocyte-associated protein-4
CV	coefficient of variation
D	day
DAA	direct-acting antiviral
DCR	disease control rate
DFS	disease-free survival
DILI	drug-induced liver injury
dL	deciliter
DNA	deoxyribonucleic acid
DOR	duration of response
E-R	exposure-response
EASL	European Association for the Study of the Liver
EC50	half-maximal effective concentration
ECG	electrocardiogram
ECOG	Eastern Cooperative Oncology Group
EDC	electronic data capture
eg	exempli gratia (for example)
eGFR	estimated glomerular filtration rate
EHR	electronic health record
EHS	extrahepatic spreading
EMR	electronic medical record
EOT	end of treatment
E-R	exposure-response
etc	et cetera

Term	Definition
EUDRACT	European Union Drug Regulating Authorities Clinical Trials Database
FDA	Food and Drug Administration
FDC	fixed-dose combination
FFPE	formalin-fixed, paraffin-embedded
FGL-1	fibrinogen-like protein 1
FSH	follicle-stimulating hormone
FU	follow-up
g	gram
GC	gastric cancer
GCP	Good Clinical Practice
GFR	glomerular filtration rate
h	hour
H&E	hematoxylin and eosin
HBsAg	hepatitis B surface antigen
HBV	hepatitis B virus
HCC	hepatocellular carcinoma
HCG	human chorionic gonadotropin
HCV	hepatitis C virus
Hep B	hepatitis B
Hep C	hepatitis C

Term	Definition
Hep D	hepatitis D
HIFU	high-intensity focused ultrasound
HIV	human immunodeficiency virus
HR	hazard ratio
IB	Investigator's Brochure
IC50	half-maximal inhibitory concentration
ICF	informed consent form
ICH	International Conference on Harmonisation
ICMJE	International Committee of Medical Journal Editors
ICOS	inducible T cell co-stimulator
ie	id est (that is)
IEC	Independent Ethics Committee
IFN- γ	interferon- γ
Ig	immunoglobulin
IgG	immunoglobulin G
IgG4	immunoglobulin G4
IHC	immunohistochemistry
IL	interleukin
IMAE	immune-mediated adverse event
IMP	investigational medicinal product
IND	Investigational New Drug
INR	international normalized ratio
IO	immuno-oncology
IP	investigational product
Ipi	ipilimumab
IRB	Institutional Review Board
IRT	interactive response technology

Term	Definition
ITT	intent-to-treat
IU	international unit
IUD	intrauterine device
IUS	intrauterine hormone-releasing system
IV	intravenous
kg	kilogram
Kd	dissociation constant
L	liter
LAG-3	lymphocyte activation gene 3
LDH	lactate dehydrogenase
LFT	liver function test
LVEF	left ventricular ejection fraction
m ²	meters squared
mg	milligram
MG	myasthenia gravis
MHC	major histocompatibility complex
mL	milliliter
MLR	mixed lymphocyte reaction
MMR	measles, mumps, rubella
mOS	median overall survival
mPFS	median progression-free survival
mRECIST	modified Response Evaluation Criteria in Solid Tumors
MRI	magnetic resonance imaging
msec	millisecond
MUGA	multiple-gated acquisition

Term	Definition
MVI	macrovascular invasion
N	number of subjects or observations
NCCN	National Comprehensive Cancer Network
NCI	National Cancer Institute
NE	not estimable
ng	nanogram
Nivo	nivolumab
nM	nanomolar
NR	not reached
NSCLC	non-small cell lung cancer
O ₂	oxygen
ORR	objective response rate
OS	overall survival
PAI	percutaneous acetic acid injection
PCR	polymerase chain reaction
PD	progressive disease
PD-1	programmed cell death-1
PD-1+	programmed cell death-1-positive
p-DILI	potential drug-induced liver injury
PD-L1	programmed death-ligand 1
PD-L2	programmed death-ligand 2
PE	physical examination
PEI	percutaneous ethanol injection
PET	positron emission tomography
PFS	progression-free survival
PFS2	progression-free survival 2

Term	Definition
PID	participant identification
PK	pharmacokinetic
PPK	population pharmacokinetics
PR	partial response
PT	prothrombin time
Q2W	every 2 weeks
Q3W	every 3 weeks
Q4W	every 4 weeks
Q6W	every 6 weeks
Q12W	every 12 weeks
R&D	research and development
RCC	renal cell carcinoma
RECIST	Response Evaluation Criteria in Solid Tumors
Rela	relatlimab
RFA	radiofrequency ablation
RNA	ribonucleic acid
RT-PCR	reverse transcription polymerase chain reaction
SAE	serious adverse event
SAP	statistical analysis plan

Term	Definition
SARS-CoV-2	severe acute respiratory syndrome coronavirus 2
SC	safety committee
SCCHN	squamous cell carcinoma of the head and neck
SD	stable disease
SDR	Safety Data Review
SI	International System of Units
SMT	Safety Management Team
SOP	standard operating procedures
SUSAR	suspected, unexpected serious adverse reaction
t1/2	half-life
T3	T3 = triiodothyronine
T4	thyroxine
TACE	transarterial chemoembolization
TAE	transarterial embolization
T.bili	total bilirubin
TCR	T-cell receptor
TKI	tyrosine kinase inhibitor
TIL	tumor-infiltrating lymphocyte
TME	tumor microenvironment
TSH	thyroid-stimulating hormone

Term	Definition
TTE	transthoracic echocardiogram
TSST	time to second subsequent therapy
UC	urothelial carcinoma
ULN	upper limit of normal
US	United States
UTN	Universal Trial Number
VEGF	vascular endothelial growth factor
VEGFR	vascular endothelial growth factor receptor
VI	vascular invasion
vs	versus
V _{ss}	mean volume of distribution at steady state
WHO	World Health Organization
WOCBP	women of childbearing potential
WNOCBP	women not of childbearing potential
WWPS	Worldwide Patient Safety

